We hypothesize that compared with standard 6-week non-weight bearing, early partial weight bearing walking at 2 weeks post-surgery improves the patient's quality of life, allows faster rehabilitation with better 1MTPJ range of motion and faster decrease in generalized swelling. This early weight bearing rehabilitation program will not negatively affect the stability of the surgical reconstruction correction and maintains a good radiological outcome as well as the traditional rehabilitation protocol where weight bearing begins at 6 weeks.

Patients and Methods

Patients

This is an open-label randomized controlled trial. We aim to recruit 50 adult (>18 yrs) patients who undergo hallux valgus by the EDSTP will be recruited. Exclusion criteria are those whom have disabilities (both physical and mental) which may impair the adherence of the rehabilitation and those who have undergone additional procedures such as concomitant 2nd toe deformity correction.

Randomization will be performed after the end of the EDSTP surgery to ensure there is no bias during the surgical procedure. Parallel groups will be allocated at 1:1 ratio via a computer generated random number, with 25 patients at each group.

In the control group, the subjects will follow the existing rehabilitation protocol of non-weight bearing walking for 6 weeks followed by heel walking for 6 weeks, followed by the resumption of normal full weight-bearing walking in normal shoes at 12 weeks post-operation. In the trial group, the subjects will begin heel walking when the bulky dressing and sutures are removed at 2 weeks post-operation and resume full weight bearing walking in normal shoes at 12 weeks post-operation. All subjects will be followed-up at 2 weeks, 6 weeks, 12 weeks, 18 weeks and 26 weeks post-operatively.

This study will be performed in the North District Hospital in Hong Kong. The study protocol will be approved by the Joint Chinese University of Hong Kong – North Territories East Cluster Clinical Research Ethics Committee and all participant will provide written informed consent. The study procedure will be conducted in compliance with Declaration of Helsinki and Good Clinical Practice (GCP) Guidelines.

Study outcomes

The primary outcomes are:

- Radiological changes including hallux valgus angle (HVA), intermetatarsal angle (IMA), and tibial sesamoid position by weight bearing feet X-Rays will be measured at 12, 18, and 26 weeks post-surgery.

Secondary Outcomes are:

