- Pain at the bunion, the first metatarsophalangeal joint (1MTPJ) and transfer metatarsalgia using the visual analogue scale will be measured at 2, 6, 12, 18, and 26 weeks post-surgery.
- Range of Motion (ROM) at 1MTPJ will be measured at 2, 6, 12, 18, and 26 weeks post-surgery.
- Foot function measured by the American Orthopaedic Foot and Ankle, Score hallux score, which ranges from 0 to 100, will be conducted at 12, 18, and 26 weeks post-surgery.
- Foot function by the self-reported Foot and Ankle Outcome Score (FAOS) questionnaire will be measured at 12, 18, and 26 weeks post-surgery. FAOS consists of 5 subscales: pain, other Symptoms, function in ADL, function in sport and recreation, and foot and ankle-related Quality of Life. The previous week is taken into consideration when answering the questionnaire. Standardized answer options are given (% Likert boxes) and each question gets a score from 0 to 4. A normalized score (100 indicating no symptoms and 0 indicating extreme symptoms) is calculated for each subscale.

Statistical analysis

All analyses will be performed in IBM SPSS Statistics, Version 20.0 (SPSS Inc, Chicago, IL, USA). Results are shown as mean \pm SD, median (interquartile range) or number (frequency) depending on the type and distribution of data. Between-group comparisons will be conducted by one-way analysis of variance (continuous normal distributed data), Mann-Whitney U test (continuous non-normally distributed data), or chi-square test (categorical data) depending on the type and distribution of data. All hypotheses are two-tailed, and p values <0.05 are considered statistically significant.

References

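### Tibial sesamoid position, a primary outcome, has no stated scale; if it is recorded in ordered grades, the analysis rule read literally selects a chi-square test that ignores their order

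*Combined protocol and SAP*

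**What the plan says.** The Study outcomes section gives the primary outcome as "Radiological changes including hallux valgus angle (HVA), intermetatarsal angle (IMA), and tibial sesamoid position by weight bearing feet X-Rays", measured at 12, 18 and 26 weeks. The two angles are plainly continuous. Nothing says whether sesamoid position is a grade, a distance or a percentage.

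The Statistical analysis section assigns tests to data types, not to outcomes. One-way ANOVA is for normally distributed continuous data. The other two routes are "Mann-Whitney U test (continuous non-normally distributed data), or chi-square test (categorical data"). The choice is made "depending on the type and distribution of data. All hypotheses are two-tailed". Ordinal data are not named. The error rate is set by "All hypotheses are two-tailed, and p values <0.05 are considered statistically significant".

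On size, the Patients section says "Parallel groups will be allocated at 1:1 ratio via a computer generated random number, with 25 patients at each group". No power calculation, effect size or expected distribution is given for any outcome.

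**The concern.** The section on hypothesis and objectives expects early weight bearing not to harm the stability of the correction. The Introduction names the feared harm as failure of the construct and early recurrence. For the sesamoid, that is a shift in one direction, towards a worse position. A chi-square test on a table of arm by grade asks whether the two distributions differ in any way, and so spreads its power over patterns the trial is not asking about. A rank test concentrates on the shift.

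The pain scores, range of motion, AOFAS score and FAOS subscales are all numeric, as are the two angles. Sesamoid position is therefore the one listed outcome that could plausibly fall under the categorical clause, and it is primary. If the text is instead taken as ambiguous, two tests of different power remain open for a primary outcome of an open-label trial, and the choice could be made after the data are seen.

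**Working it through.** **Figure to reproduce.** None. The documents give a sample size without a power calculation.

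**Inputs from the documents.** 25 per arm; two-sided 0.05; the three tests and the data types they serve.

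**Inputs assumed.** 3, 4 or 7 ordered grades; several control distributions for each (even, and skewed or peaked); a proportional-odds shift with odds ratio (OR) 1 to 5; no dropout; one comparison at one visit.

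**Method.** If c is the control arm's cumulative probability up to a grade, the other arm has odds c/(1−c) divided by OR at that grade. Each scenario used 20,000 simulated trials, comparing the Pearson chi-square test on the 2 × k table with the tie-corrected Mann-Whitney test (normal approximation).

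**One scenario by hand: 4 even grades, OR 3.**
- Control cumulative probabilities are 0.25, 0.50, 0.75, with odds 1/3, 1, 3. Dividing by 3 gives 1/9, 1/3, 1, so the other arm's cumulative probabilities are 0.10, 0.25, 0.50.
- Grade probabilities are 0.25, 0.25, 0.25, 0.25 against 0.10, 0.15, 0.25, 0.50. Mean totals per grade in 50 patients are 8.75, 10, 12.5, 18.75.
- Chi-square noncentrality is the sum of (difference in counts)²/total: 3.75²/8.75 + 2.5²/10 + 0 + 6.25²/18.75 = 1.607 + 0.625 + 0 + 2.083 = 4.315. On 3 df with critical value 7.81, power is about 38%.
- For Mann-Whitney, the probability that a patient in the shifted arm is worse, counting ties as half, is 0.10×0.125 + 0.15×0.375 + 0.25×0.625 + 0.50×0.875 = 0.6625. The mean shift in U is 625 × 0.1625 = 101.6. The tie-corrected null variance is (625/12) × (51 − 10164.8/2450) = 2440, so the SD is 49.4 and z = 101.6/49.4 = 2.06. Power is about 54%.
- Simulation gives 37.9% and 55.1%, a loss of 17.2 points.

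**Simulated loss of power (Mann-Whitney minus chi-square, percentage points, range over the assumed control distributions).**

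| Grades | OR 1.5 | OR 2 | OR 3 | OR 4 | OR 5 |
|---|---|---|---|---|---|
| 3 | 2.1–2.3 | 5.7–6.3 | 10.1–10.7 | 10.5–10.8 | 8.9–9.3 |
| 4 | 3.6–4.6 | 9.2–10.1 | 17.2–18.0 | 17.7–18.6 | 15.0–15.3 |
| 7 | 5.9–6.9 | 15.3–16.4 | 30.7–32.0 | 33.3–35.1 | 29.3–30.9 |

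At OR 3 the underlying powers are 42–43% against 52–53% (3 grades), 36–38% against 53–56% (4 grades) and 26–27% against 57–58% (7 grades). With no shift, rejection rates were 3.3–5.0% for chi-square and 4.8–5.1% for Mann-Whitney, so the rank test does not gain by inflating type I error.

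**Sparse cells.** With equal arms, an expected count is below 5 whenever a grade holds fewer than 10 of the 50 patients. At least one grade did so in 59–100% of 4-grade tables and essentially all 7-grade tables. With 3 grades it was 4–98%, depending on the distribution and effect. In the hand example the lowest grade already has an expected count of 8.75/2 = 4.4. The plan names no exact alternative.

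**The opposite case.** Against a pure difference in spread, such as 0.20, 0.30, 0.30, 0.20 against 0.45, 0.05, 0.05, 0.45, chi-square has 93% power and Mann-Whitney 7%.

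**The case against.** The strongest reply is that the documents never say the outcome is graded and never assign it to chi-square. It could be measured as a distance or percentage. Mann-Whitney is already in the plan, as is the median with interquartile range, and an analyst could treat a numeric grade as a score and use it. This stands: the gap is an undefined scale and an unassigned test, not a stated wrong test. It does not close the gap, because the wording confines Mann-Whitney to continuous data, so using it on grades departs from the rule as written.

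A reader might infer that the plan carries a fixed and large power loss. The documents do not support this. They give no number of grades, distribution or effect size, and with few grades or a small shift the loss is only a few points. Nor is chi-square always the weaker test on graded data, as the spread example shows.

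A reader might also infer that the choice of test is what makes a non-significant result uninformative about harm. That difficulty comes mainly from the lack of a margin or an interval-based comparison, and it affects the two angles equally. At OR 3, Mann-Whitney itself has only 52–58% power in these scenarios.

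**Conclusion.** The point holds conditionally. The scale of a primary outcome is undefined, and if it is an ordered grade, the literal rule selects a test that discards the order. Given a one-directional proportional-odds shift, 25 per arm and no dropout, the cost is about 10 to 11 points of power with 3 grades, 17 to 19 with 4 and 31 to 35 with 7 at odds ratios of 3 to 4. It falls to about 6 to 16 points at an odds ratio of 2 and 2 to 7 at 1.5. If the position is measured on a continuous scale, there is no loss of this kind. Correcting the test sharpens one comparison; it does not supply the evidence needed to claim that early weight bearing does no harm. The change is worth making because it concerns a primary outcome and costs almost nothing.

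**What to change.** State in Study outcomes how tibial sesamoid position is recorded: the scale, the number of levels and which direction is worse. If it is ordered, state in Statistical analysis that it is compared by Mann-Whitney and reported with a common odds ratio, or another ordinal effect estimate, and its 95% CI. Adjust for baseline grade only if a pre-operative film is available; the listed films are at 12, 18 and 26 weeks only. Keep chi-square, or an exact test where counts are small, for unordered or binary data.

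The cost is one or two sentences, with no extra patients or visits. What is given up is power against non-monotone differences. That loss can be large for a pure change in spread, but such a change is not the pattern the trial is concerned with.
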